10.1 Subject Disposition

10.1.1 Screening

Number and details (inclusion and exclusion criteria) of screened but not included patients are centrally recorded in a separate database (Research Electronic Data Capture; <https://www.project-redcap.org>) of the Department of Anaesthesiology and Pain Medicine (KAS) at the Bern University Hospital.

10.1.2 Randomization

Sites were randomly allocated to sequences of interventional and control phases before study begin. Subsequently, a calendar with dates defining intervention and control phases for each site was set. Patients were allocated by the study personal to the control or intervention group [cdds_phase] depending on the date they presented to the ED.

10.1.3 Non completion

Reasons for non-completion of the study [non_comp_reason] are documented with following categories:

- 1 Patient withdrew consent
- 2 Patient was lost to follow-up
- 3 Patient was excluded requested by PI
- 4 Patient was excluded due to SAE
- 5 Patient died
- 88 Other reason

Patients who died before follow-up will not be considered as lost to follow-up. All others will be considered as lost to follow-up or drop outs.

10.1.4 Reporting

The study design is a cluster randomized cross-over trial, however, in- and exclusion criteria were set on subject (i.e patient) and not on group (i.e site) level and subjects included in one period only. Therefore, we deemed a flow diagram on subject level following the CONSORT Flow Diagram for a parallel-randomized trial as appropriate. However, we will additionally present supplemental figures showing inclusion rates over time for the individual clusters.

Period [period]	
The number of period is derived from the patient's date of signed informed consent [ic_date] and beginning of the respective period as pr-especified for each site.
 
  
 Startdate	Period	1	2	3	4	5	6	
   
 Tiefenau	06.06.2022	08.08.2022	10.10.2022	12.12.2022	13.02.2023	17.04.2023	
 
 Insel	13.06.2022	15.08.2022	17.10.2022	19.12.2022	20.02.2023	24.04.2023	
 
 Solothurn	20.06.2022	22.08.2022	24.10.2022	26.12.2022	27.02.2023	01.05.2023	
 
 Muensingen	27.06.2022	29.08.2022	31.10.2022	02.01.2023	06.03.2023	08.05.2023	
  
	Startdate	Period	1	2	3	4	5	6	Tiefenau	06.06.2022	08.08.2022	10.10.2022	12.12.2022	13.02.2023	17.04.2023	Insel	13.06.2022	15.08.2022	17.10.2022	19.12.2022	20.02.2023	24.04.2023	Solothurn	20.06.2022	22.08.2022	24.10.2022	26.12.2022	27.02.2023	01.05.2023	Muensingen	27.06.2022	29.08.2022	31.10.2022	02.01.2023	06.03.2023	08.05.2023
Startdate	Period	1	2	3	4	5	6																														
Tiefenau	06.06.2022	08.08.2022	10.10.2022	12.12.2022	13.02.2023	17.04.2023																															
Insel	13.06.2022	15.08.2022	17.10.2022	19.12.2022	20.02.2023	24.04.2023																															
Solothurn	20.06.2022	22.08.2022	24.10.2022	26.12.2022	27.02.2023	01.05.2023																															
Muensingen	27.06.2022	29.08.2022	31.10.2022	02.01.2023	06.03.2023	08.05.2023																															
Charlson-comorbidity index [cci]	
The CCI is a score of comorbid conditions that are each weighted from 1 to 6 based on disease severity. Definition of disease severity follows Kim et al. (2014) (6) and derived from following variables:
 
[cci_mi], [cci_chf], [cci_pvd], [cci_cva], [cci_dementia], [cci_copd], [cci_ctd], [cci_pud], [cci_hemi], [cci_ckd], [cci_leuk], [cci_lymph], [cci_aids], [cci_liver], [cci_dm], [cci_dm_2], [age]
																																				
Tracked CDDS usage	Number and timing of queries (relative to ED entry) and number of entered symptoms are derived from [cdds_request_datetime], [cdds_user], [cdds_input_symptoms]. Duplicated queries (no differences in entered symptoms) will not be considered.																																				

10.3 Protocol Deviations

Protocol deviations are considered major if the CDDS were not used during interventional periods or used during control periods. This protocol deviations are addressed by the PP-analysis and sub-analysis described in section **Fehler! Verweisquelle konnte nicht gefunden werden.** and **Fehler! Verweisquelle konnte nicht gefunden werden.** Follow-up phone interviews may have been conducted after 14±4 days because some patients returned the call after the timeframe or specifically requested a call to on one of the subsequent days. We will perform a primary efficacy sensitivity analysis without these patients if the number of cases exhibits more than 5%. We do not expect any other protocol deviations that may interfere with the primary efficacy analysis.

10.4 Demographic and Baseline Variables

All baseline variables as specified in 7.5.4 Covariates

10.5 Concurrent Illnesses and Medical Conditions

Diagnoses will be classified according to clinical modification of the International Statistical Classification of Diseases and Related Health Problems (ICD-10 GM)

10.6 Treatment Compliance

Number of queries and the average number of symptoms entered into the DDx generator per patient will be used for treatment compliance. In addition, self-reported usage of CDDS outside the study protocol [othercdds1] will be reported.

11 Efficacy Analyses

Data will be summarized by treatment groups. N, mean and standard deviation will summarize continuous efficacy variables, whereas number and percent will summarize categorical efficacy variables. Statistical analyses will be based on multi-level general linear mixed modelling (GLMM) methods using appropriate post hoc techniques (e.g for subgroup analyses). Regression coefficients for continuous endpoints and odds ratios for binary endpoints and geometric mean ratios for ln-transformed continuous outcomes will be displayed as measure of strength accompanied by their 95% confidence intervals. Viewing plots along with normality testing (e.g. Shapiro-Wilk) will be used in order to check assumptions for the appropriate use of parametric testing approaches. Transformations to normality for variables not fulfilling normality assumptions will be considered (e.g. log, Box-Cox etc.), while nonparametric testing using counterparts of ad-hoc parametric procedures will also be an option as needed (e.g. Kruskal-Wallis instead of one-way ANOVA, the latter being part of the GLM family). R (R Foundation for Statistical Computing, Vienna, Austria) will be used for data analysis. A test-wise 2-sided p-value of less than 0.05 will be considered statistically significant.

11.1 Primary Efficacy Analysis

For the primary binary outcome, presence or no presence of a diagnostic quality risk, a generalized linear mixed model (GLMM) with a binomial distribution family and exchangeable correlation structure will be performed. The GLMM takes into account a random intercept for each site, resident and attending physician. In some cases, patients may be treated by more than one resident or attending physician due to changes in shift. The physicians who were initially involved in treatment will be selected as diagnosing physicians. The condition (intervention and control) and the period (period 1 to 6) will be included as fixed factors under the assumption of equality of carry-over effects. Additionally, chief complaint, age, sex and Charlson Comorbidity Index will be added as covariates. The primary efficacy analysis will be performed on the ITT set.

11.2 Secondary Efficacy Analyses

11.2.1 Secondary Analyses of Primary Efficacy Endpoint

a) *Per Protocol:*

The same model as for the primary efficacy analysis will be performed on the PP set.

b) *Sensitivity analyses:*

Sensitivity analysis will follow the primary efficacy analysis with or without adjustments in model specification.

- GLMM on multiple imputed data (if missing >5%)
- GLMM without baseline covariates
- GLMM with site as fixed factor
- LMM without random effects
- Robust GLMM
- Generalized Estimating Equations to compare against GLMM

c) *Compliance:*

An additional sub-analysis on the PP set will be performed after excluding patients from the intervention group if none of the CDDS query included more than three entered symptoms/clinical features.

11.2.2 Analyses of Secondary Endpoints

Secondary endpoints will be analysed using the ITT set.

a) *Death*

The same model as for the primary efficacy analysis will be performed.

b) *Unscheduled medical care*

The same models as for the primary efficacy analysis will be performed.

c) *Unexpected Intensive Care Unit admission*

The same model as for the primary efficacy analysis will be performed.

d) *Diagnostic discrepancy between ED diagnosis and diagnosis at follow-up*

The same model as for the primary efficacy analysis will be performed.

e) *Length of ED stay*

A generalized linear model (GLM) will assess the treatment effect on patients' LOS [hours] in the ED.

LOS are count data and hence, models based on normal distribution are not appropriate. (7)

Instead, we will apply a Poisson and a negative binomial regression model to select the better performing model based on dispersion and AIC. Following variables will be included in the model as independent variables: treatment, site, period, age, sex, chief complaint, Charlson comorbidity index, admission type. As sensitivity analyses, we will perform a linear regression model after log transforming the dependent variable.

f) *Length of hospital stay*

Analyses will parallel length of ED stay.

g) *Diagnostic tests in ED*

The same model as for the primary efficacy analysis will be performed to assess the treatment effect on likelihood of performed diagnostic test for each the following categories: blood, urine, sputum, MRI, CT, Sonography and x-ray. Subcategories will be analyzed descriptively.

h) *ED resource consumption (ED costs)*

A GLMM will be performed to assess treatment effect on costs. The dependent variable will be natural log transformed to account for skewness. Period and site as well as patients' age, sex, chiefcomplaint, Charlson Comorbidity Index, triage level and admission type will be added as covariates.

A sensitivity sub-analysis without patients from the Bürgerspital Solothurn will be performed as the administrative accounting data may somewhat differ compared to the other hospitals.

i) *Total resource consumption (total costs)*

The analyses for total resource consumptions follows the analyses for ED resource consumption (see h)

j) *Diagnostic tests after ED*

Diagnostic tests during unscheduled medical care after ED/Hospital discharge will be analyzed using descriptive statistics (counts and proportions).

k) *Discharge destination*

Discharge destination will be analyzed using descriptive statistics. Whether the intervention has an effect on inpatient admission or discharge at home is assessed with the analysis on length of hospital stay (see *length of hospital stay* above).

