7.4 Study Assessments

Investigation Periods	Screening	Consent (ICF)	Treatment, Intervention Period		Follow-up
Emergency care in the emergency room	Admittance and triage	Waiting time	Medical examination and treatment		discharged or hospitalized
Time	-1 to -5h	-1 to -5h	0 to 1h	1h + LOS	14d±4d
A) Enrolment					
In- /Exclusion criteria	x				
Patient information		x			
Patient consent (ICF)		x			
B) Intervention					
CDDS application during intervention period			x	(x)	
CDDS usage monitoring by study nurses			x		
C) Assessments (CR: performed within clinical routine as appropriate)					
Demographics	x				
Chief complaint	CR				
Triage assessment	CR				
Medical history			CR		
Physical examination			CR	CR	
Vital signs			CR	CR	
Laboratory tests			CR	CR	
Other diagnostic tests			CR	CR	
CDDS input / output data collection			x	(x)	
Physician questionnaire			x	(x)	
Patient telephone interviews					x
Medical record review from ED, hospital and/or GP			x	x	x
Serious Adverse Events, Adverse device effects			x	x	x
Device Deficiencies			x	x	
D) Primary Outcome Score					
All-cause mortality					x
Unscheduled medical care if discharged (GP, ED revisit, hospitalization)					x
Unexpected ICU admission or upscale in care within 24h if hospitalized					x
Current diagnosis for presenting complaint				x	x
E) Secondary Outcomes					

Number and cost of ED diagnostic tests				x	x
Time to ED diagnosis				x	
ED differential diagnoses				x	
Physician confidence in ED diagnosis				x	
Discharge destination				CR	
ED LOS				CR	
Hospital LOS if hospitalized					CR
CDDS usage (number of queries)		x	(x)		
Patient reported outcomes					x

ED, Emergency room; ICU, intensive care unit; CDDS, computerized diagnostic decision support system; GP, general practitioner; LOS, length of stay; CR, clinical routine

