7.5.2 Secondary endpoints

Variables	Description	Scale	Time Window*
Death	see primary endpoint above	0, no 1, yes	14±4 days
Unscheduled medical care	see primary endpoint above	0, no 1, yes	14±4 days
Unscheduled medical care	see primary endpoint above	0, no 1, yes	7 days
Unscheduled medical care	see primary endpoint above	0, no 1, yes	3 days
Unexpected Intensive Care Unit admission	see primary endpoint above	0, no 1, yes	24h
Diagnostic discrepancy between ED diagnosis and diagnosis at follow-up	see primary endpoint above	0, no 1, yes	14±4 days
Length of ED stay	Time difference between ED admittance to ED discharge or ward admission	number of hours (ranging from 0 up to 24 hours)	up to 24 hours after ED discharge
Length of hospital stay if hospitalized	Days between ward admission and hospital discharge	number of days ranging from 0 days (discharged at admission day) to 18 days (if hospitalized at end of follow-up)	up to 18 days
Diagnostic tests in ED	Data are sought from the EHR to indicate if the patient received one of the following diagnostic tests during the ED stay: laboratory (blood, urine or sputum), MRI, CT, sonography, x-ray, other. Data is collected for each diagnostic type and corresponding subgroups (e.g abdominal CT, head CT etc.)	0, no 1, yes	length of ED stay, up to 24 hours
ED resource consumption (costs)	Hospitals administrative cost accounting data will be used as a measure of costs that were caused during patient's ED stay. Total costs and subcategories of the cost unit accounting are collected.	numeric in Swiss Francs (CHF)	length of ED stay, up to 24 hours
Total resource consumption (costs)	Hospitals administrative cost accounting data will be used as a measure of costs that were caused during patient's ED and hospital stay if hospitalized. Total costs and subcategories of the cost unit accounting are collected.	numeric in Swiss Francs (CHF)	length of hospital stay, up to 24 hours
Diagnostic tests after ED	Data are sought from the EHR, GP or patient reported during follow-up to indicate if the patient received one of the following diagnostic tests on one of the medical appointments (see care consumption above). laboratory (blood, urine or sputum), MRI, CT, sonography, x-ray, other	0, no 1, yes	14±4 days
Discharge destination	Discharge from ED to one of following locations	0, home 1, hospital (intern) 2, hospital (extern) 3, nursing home 4, rehabilitation 88, other	length of ED stay, up to 24 hours

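### Diagnostic tests after the ED are defined in SAP 7.5.2 over the patient's medical appointments without restriction, but 11.2.2 j) analyses only those at unscheduled care

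*SAP*

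**What the plan says.** The definition is in 7.5.2, row on diagnostic tests after the ED. Information from the EHR, the GP or the patient is used to establish whether "the patient received one of the following diagnostic tests on one of the medical appointments (see care consumption above". The scale is yes/no and the window 14±4 days. Nothing in the row limits it to unscheduled appointments.

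The analysis is in 11.2.2 j): "Diagnostic tests during unscheduled medical care after ED/Hospital discharge will be analyzed using descriptive statistics", as counts and proportions. No denominator is named.

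For tests during the ED stay, 7.5.2 uses the EHR "to indicate if the patient received one of the following diagnostic tests during the ED stay", again yes/no. Section 11.2.2 g) applies the primary model to the "likelihood of performed diagnostic test for each the following categories: blood, urine, sputum, MRI, CT, Sonography and x-ray" and adds that "Subcategories will be analyzed descriptively". The schedule in 7.4 labels the corresponding row "Number and cost of ED diagnostic tests".

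**The concern.** Section 11.2.2 j) covers only part of what 7.5.2 defines. The part it keeps is selected by an event that follows allocation and that the intervention is meant to influence, because unscheduled care is one of the four components of the primary endpoint.

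Two distortions follow. Work-up moved from the ED to a planned outpatient visit is not counted. And if the CDDS reduces unscheduled visits, the tests done at them fall too, whether or not patients are tested less overall. In either case the table could look like neutral or reduced testing after the ED when testing has only changed place. Economic implications are a stated secondary objective (6.1), so the table will be read in that light.

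**Working it through.** The SAP gives no frequency for tests after the ED, so there is no figure to reproduce. The check sets the sections side by side and then follows the consequence algebraically.

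**1. Is j) narrower than 7.5.2?** Section 10.2 derives unscheduled care from documented appointments that were unplanned [cc_type_exp] and related or probably related to the index visit [cc_type_rel]. Documented appointments therefore include planned ones, and j) takes a subset.

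**2. Does the cross-reference settle the scope?** The 7.5.2 row points to a care consumption entry above it. No such row exists in 7.5.2. Section 6.2 lists care consumption after ED discharge as an endpoint of its own, separate from the components of the primary endpoint. Section 11.2.2 has no analysis under that name.

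**3. Does another analysis cover testing after discharge?** Section 11.2.2 g) covers the ED stay. The costs in h) and i) are, by 7.5.2, those of the ED stay and of the ED plus hospital stay. Neither reaches appointments after discharge, so j) stands alone.

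**4. How does j) behave?** Let u be the proportion of patients with unscheduled care, t the probability of a test given such care, and s the proportion tested at planned visits only.

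- With all patients as denominator, j) reports J = u × t, while the definition in 7.5.2 corresponds to J + s.
- If t is equal in both conditions, J(intervention) / J(control) = u(intervention) / u(control). The level of t cancels, so no test frequency is needed.
- Illustration: section 8 assumes 12% positive on the composite under control and a difference of 5 points, hence 7% under the hypothesised benefit. If unscheduled care fell in that same ratio, 7/12 = 0.58, and J would fall by 1 − 0.58 = 42% with testing per visit unchanged. The 12% belongs to the composite; the SAP gives no rate for unscheduled care, so this is an assumption.
- If a proportion d of patients have the same test at a planned instead of an unscheduled visit, J falls by d, s rises by d and J + s is unchanged. Section 11.2.2 j) would show a reduction of d.
- If ED work-up moves to planned visits, s rises and J does not. Section 11.2.2 j) would show no difference.
- If the denominator were instead patients with unscheduled care, j) would report J / u = t. The mechanical fall disappears, but the comparison is then between patients selected by a post-allocation event, and planned visits are still left out.

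**The case against.** The best defence is that j) may say what 7.5.2 meant. The only appointment-based rows above the one in question are those on unscheduled medical care, so the broken reference could have been intended for them. That reading is possible and cannot be excluded. Against it, 6.2 lists care consumption separately, the wording in 7.5.2 carries no restriction, and appointments are flagged as unplanned or not. The scope is at best unresolved, and even the narrow reading leaves the table hard to interpret.

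It is also fair to say that j) is descriptive, tests nothing and makes no claim that testing shifted out of the ED, and that costs are modelled in h) and i). All of that stands and limits the weight of the point. The costs, however, end with the index stay.

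A reader might go further and infer from the 7.4 label that the ED analysis is also wrong, or that the plan cannot show whether the CDDS changes testing. The document does not support this. Section 6.2 refers to 7.5 for the specification of endpoints, 7.5.2 sets ED tests as yes/no by type, and g) follows it except that the category for other tests has no model. The seven models estimate an adjusted effect on each type. Replacing them with a total would be a trade-off: under an assumed rise of 6 points in CT and fall of 6 points in sonography the total does not move, while the separate categories do. Section 7.5.2 says "Data is collected for each diagnostic type and corresponding subgroups", but on a yes/no scale, so a sum over subgroups would still miss repeats of the same test.

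**Conclusion.** The point holds for tests after the ED. Sections 7.5.2 and 11.2.2 j) differ in scope, the reference that might reconcile them leads nowhere, and the narrower version depends on a post-allocation event within the primary endpoint. Its figure moves in proportion to unscheduled care when testing per visit is constant, and is blind to planned work-up. The size in this trial cannot be derived, because the SAP gives no frequency of planned visits or of tests.

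The consequence is confined to one secondary, descriptive endpoint. The primary analysis and the ED test models in g) are not affected. For ED tests, the most that follows is that the 7.4 label should be brought into line with the yes/no definition.

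The conclusion assumes that tests were recorded for planned as well as unplanned appointments, as 7.5.2 implies.

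**What to change.** Before the efficacy analyses, at the final SAP revision foreseen in 9.1:

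- In 11.2.2 j), report by condition the number and proportion of patients with each type of test at all documented post-ED appointments, split into scheduled and unscheduled using [cc_type_exp]. Use all ITT patients with follow-up as denominator. State whether the relatedness flag [cc_type_rel] applies, and apply it alike to both parts.
- In 7.5.2, replace the broken reference, either by adding a care consumption row or by naming the appointment variables directly.
- If tests at planned appointments turn out not to have been recorded, say so in 7.5.2 and j), and state that the table cannot speak to a shift towards planned work-up.
- In 7.4, align the label for ED tests with the yes/no definition in 7.5.2.

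The cost is wording and a slightly longer descriptive table. The planned/unplanned flag already exists, and no model or sample size changes.

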6.1 Study Objectives

The overall objective of this research project is to reveal the intended and unintended micro-, meso- and macro-level consequences by providing a differential diagnoses (DDx) generator (computerized diagnostic decision support system; CDDS) to physicians in an ED.

The primary (micro-level) objective is to assess the effect of the DDx generator usage on diagnostic quality in patients admitted to the ED. Our primary hypothesis is that ED patients will have a slightly but significant reduced diagnostic quality risk when physicians are asked to consult the provided DDx generator after the first physical examination.

Secondary objectives are

- on the micro-level, to investigate how the use of a DDx generator affects patient related outcomes such as mortality, length of stay, or unscheduled revisits.
- on the meso-level, to understand how DDx generator affect diagnostic workflow in the ED and physicians' advice seeking, collaboration and confidence calibration.
- on the macro-level, to investigate the economic implications of DDx generators utilization in ED and to evaluate the educational implications for physician training.

The safety objective corresponds to the primary outcome, namely how the use of a DDx generator affects diagnostic safety in patients admitted to the ED.

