18.3 Table 2 – Primary and secondary efficacy outcomes

	Intervention Group		Control Group		Measure of effect	Adjusted effect (95% CI)	p value
	N	n (%) or median (IQR)	N	n (%) or median (IQR)			
Primary outcome							
Diagnostic quality risk	XXX	XX (XX%)	XXX	XX (XX%)	OR	X-XX (X-XX to X-XX)	<X-XXX
Secondary outcomes							
Death	XXX	XX (XX%)	XXX	XX (XX%)			
Unscheduled medical care	XXX	XX (XX%)	XXX	XX (XX%)	OR	X-XX (X-XX to X-XX)	<X-XXX
Unscheduled medical care within 7 days	XXX	XX (XX%)	XXX	XX (XX%)	OR	X-XX (X-XX to X-XX)	<X-XXX
Unscheduled medical care within 3 days	XXX	XX (XX%)	XXX	XX (XX%)	OR	X-XX (X-XX to X-XX)	<X-XXX
Unexpected ICU admission or upscale in care	XXX	XX (XX%)	XXX	XX (XX%)	OR	X-XX (X-XX to X-XX)	<X-XXX
Diagnostic discrepancy	XXX	XX (XX%)	XXX	XX (XX%)	OR	X-XX (X-XX to X-XX)	<X-XXX
ED costs in CHF	XXX	XX (XX to XX)	XXX	XX (XX to XX)	GMR	XX (XX to XX)	<X-XXX
Total hospital costs in CHF	XXX	XX (XX to XX)	XXX	XX (XX to XX)	GMR	XX (XX to XX)	<X-XXX
Safety Outcomes							
Serious adverse event (overall)	XXX	XX (XX%)	XXX	XX (XX%)			
Death							
Life-threatening illness or injury	XXX	XX (XX%)	XXX	XX (XX%)			
Permanent disability / incapacity	XXX	XX (XX%)	XXX	XX (XX%)			
Medical or surgical intervention to prevent life-threatening illness	XXX	XX (XX%)	XXX	XX (XX%)			
Injury or permanent impairment	XXX	XX (XX%)	XXX	XX (XX%)			
Congenital anomaly / birth defect	XXX	XX (XX%)	XXX	XX (XX%)			
Chronic disease	XXX	XX (XX%)	XXX	XX (XX%)			
Hospitalization or prolongation of existing hospitalization	XXX	XX (XX%)	XXX	XX (XX%)			

OR, Odds Ratio; GMR, Geometric Mean Ratio; ICU, intensive care unit; ED, Emergency department, CHF, Swiss Francs

18.4 Table 3 - Full-case review for diagnostic errors in a random subset. Items of the Safer Dx instrument compared between patients not randomly

		50 random patients with diagnostic quality risk	50 random patients without diagnostic quality risk	p value
Item 1	The documented history was suggestive of an alternate diagnosis, which was not considered in the diagnostic process.	XX (XX to XX)	XX (XX to XX)	<X-XXX
Item 2	The documented physical exam was suggestive of an alternate diagnosis, which was not considered in the diagnostic process.*	XX (XX to XX)	XX (XX to XX)	<X-XXX

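### The only adjusted comparison of costs is a geometric mean ratio, which need not match the ratio of mean costs that the economic objective needs

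*SAP*

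**What the plan says.** SAP section 6.1 sets a macro-level objective "to investigate the economic implications of DDx generators utilization in ED". Section 7.5.2 defines two cost endpoints per patient in Swiss francs. For the ED endpoint, "Hospitals administrative cost accounting data will be used as a measure of costs that were caused during patient's ED stay"; the total-cost endpoint adds the hospital stay for those admitted.

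The analysis of ED costs is in section 11.2.2 h). It is a model called a GLMM, with period, site, age, sex, chief complaint, Charlson index, triage level and admission type as covariates. Of the outcome it says: "The dependent variable will be natural log transformed to account for skewness". No random effects are named there. Section 11.2.2 i) adds: "The analyses for total resource consumptions follows the analyses for ED resource consumption (see h").

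The introduction to section 11 fixes the effect measure: "geometric mean ratios for ln-transformed continuous outcomes will be displayed as measure of strength accompanied by their 95% confidence intervals". Table 2 (section 18.3) carries this through. Both cost rows have GMR as the measure of effect, with CI and p value (its footnote reads "OR, Odds Ratio; GMR, Geometric Mean Ratio"), and groups are summarised as "n (%) or median (IQR"). The only cost sensitivity analysis changes the patients and not the scale: "A sensitivity sub-analysis without patients from the Bürgerspital Solothurn will be performed".

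The same introduction to section 11 has a general rule that continuous efficacy variables are summarised by N, mean and SD per treatment group. No adjusted mean difference, ratio of arithmetic means, retransformation to CHF or log-link cost model is specified.

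**The concern.** An economic objective is ordinarily answered by the mean cost per patient, because the mean times the number of patients gives total spending. Neither a geometric mean nor a median has that property. If the tool changes costs mainly in a minority, for instance through extra imaging or a changed admission decision, the expensive tail moves more than the typical patient. The mean follows the tail, while the log scale compresses it.

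The SAP gives reason to allow for such a pattern. Section 11.2.2 g) tests for effects on individual diagnostic tests, and section 11.2.2 k) asks whether the intervention affects admission versus discharge home. Total cost therefore combines a cheaper and a dearer group whose proportions the intervention may alter. At stake is the published economic statement: a GMR close to 1 could be read as no effect on costs, or a GMR below 1 as a saving, when mean cost per patient says something different.

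**Working it through.** **Inputs.** The SAP states no cost mean, SD, effect size or power, so there is no figure of its own to reproduce. The log-scale SDs and CHF amounts below are assumptions. The group size for the simulation comes from section 8: 1184 patients with 10% loss gives 1184 × 0.9 / 2 ≈ 533 per condition.

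**Relation between the two measures.** If log cost is normal with mean μ and SD s, the geometric mean is exp(μ) and the arithmetic mean is exp(μ + s²/2). With s1 for intervention and s0 for control:

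ratio of means = GMR × exp((s1² − s0²)/2)

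**Ratio of means when the GMR is exactly 1.00 (assumed SDs, control vs intervention).**
- 0.8 vs 0.8: exp(0) = 1.00
- 0.8 vs 0.9: exp((0.81 − 0.64)/2) = exp(0.085) = 1.09
- 1.0 vs 1.1: exp((1.21 − 1.00)/2) = exp(0.105) = 1.11
- 1.0 vs 1.2: exp((1.44 − 1.00)/2) = exp(0.22) = 1.25

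The discrepancy can also run the other way. With 1.0 vs 1.2 and equal means, the GMR would be exp(−0.22) = 0.80, an apparent saving that does not exist.

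**What a test would show.** The simulation used two groups of 533, lognormal costs, equal geometric means, no clustering and no covariates, with 3,000 runs. It recorded how often each test rejected at the two-sided 5% level.
- 1.0 vs 1.1: log-scale test about 5% (its null level), test of mean cost about 22%
- 1.0 vs 1.2: log-scale test about 5%, test of mean cost about 62%

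**Without lognormality.** These are simple cases in which only some patients are affected.
- Costs of 5% of otherwise typical patients tripled: GMR = 3^0.05 = 1.06; if all patients start at the same cost, ratio of means = 1 + 0.05 × 2 = 1.10.
- Costs of 10% of otherwise typical patients doubled: GMR = 2^0.10 = 1.07; ratio of means = 1 + 0.10 × 1 = 1.10.
- 90% at CHF 1000 and 10% at CHF 20000, mean 2900. The tail doubles and the others fall by the factor 2^(−1/9) = 0.926: GMR = 1.00, mean = 0.9 × 926 + 0.1 × 40000 ≈ 4833, ratio 1.67.

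In the first two cases the GMR moves in the right direction but understates the change. In the third it is null, but only because a fall of about 7% in the other patients offsets the tail.

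**Comparison within the SAP.** For length of stay, also skewed, section 11.2.2 e) chooses Poisson or negative binomial regression, which model the arithmetic mean, and makes the linear model on the log scale the sensitivity analysis. For costs, the log-scale model is the main analysis and no mean-based model is given.

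**The case against.** A reader might infer that costs are compared by GMR and nothing else, or that the SAP's analysis will conceal a cost increase. The document does not support either reading.

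- **Means are not wholly absent.** The general rule in section 11 provides for mean and SD by group, and table layouts may change. What is missing is narrower: an adjusted comparison of means with a CI. The rule is descriptive, and Table 2 as laid out shows medians.
- **The target is partly inferred.** Section 6.1 speaks of economic implications and names no mean-cost, budget-impact or cost-effectiveness estimand. A log-scale model is a common and valid analysis of skewed costs. It estimates a different quantity, and nothing in the SAP is contradicted.
- **Other analyses would reveal part of the effect.** Sections 11.2.2 e) to g) test ED stay, hospital stay (zero days if not admitted, section 10.2) and the main diagnostic tests. These bear directly on the feared mechanism. They are not in CHF, so they reduce the gap without closing it.
- **The percentages are illustrations.** They hold the GMR at exactly 1 with chosen SDs. As the first two unequal-effect cases show, attenuation is often more plausible than a null GMR.
- **Replacing the model is not called for.** Section 11.2.2 h) names no random effects to carry over, and with four sites a robust or bootstrap interval needs thought. Adding an estimate is enough.

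Section 11.3 permits further labelled exploratory analyses, but none on mean cost is pre-specified. The SAP refers to no separate economic plan, though one may exist.

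**Conclusion.** The point holds in this form: for both cost endpoints, the only planned comparison that is adjusted and carries a CI and p value is a GMR. It is presented beside medians, while the objective it serves is best answered by mean cost per patient.

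The two measures are bound to agree only if the intervention shifts log cost without changing its spread or shape. The SAP neither states nor plans to check this, and it is doubtful for total costs. Differences of 9% to 25% in mean cost at a GMR of 1.00 are possible under the assumed SDs. The true divergence cannot be sized from the SAP and may be nil. This is a worthwhile, inexpensive improvement to a secondary endpoint and has no bearing on the primary conclusion.

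**What to change.** For ED costs and total costs, pre-specify an adjusted difference in CHF and a ratio of arithmetic mean cost, each with a 95% CI. A gamma model with log link would serve. It would use the covariates already listed in section 11.2.2 h), site and period included, followed by marginal standardisation: predict every patient's cost under each condition, average the predictions, and take the difference and ratio.

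State the CI method and, if bootstrapped, the resampling unit. Four sites are too few to resample reliably. Condition varies only between the 4 × 6 = 24 site-by-period cells, so resampling patients within cells would ignore variation between cells. Whichever choice is made, its limitation should be stated.

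Keep the GMR and report the mean-based estimates beside it. Show mean (SD) next to median (IQR) in the cost rows of Table 2. State that any conclusion on economic impact rests on the mean-cost estimate.

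The cost is a little more analysis work and wider intervals where costs are heavy-tailed. No new data are needed.
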